Primary endpoint: Clinical effectiveness measured in terms of technical and clinical success.

Technical success was defined as defined on an intent-to-treat basis and requires the successful introduction and deployment of the device in the absence of surgical conversion or mortality, type I or III endoleaks, or graft limb obstruction. A technical success thus implies the following qualifying details: 1. Successful access to the arterial system using a remote site (ie, the femoral, external iliac, common iliac, or brachiocephalic arteries with or without the use of a temporary or permanent prosthetic conduit to access these arteries); 2. successful deployment of the endoluminal graft with secure proximal and distal fixation; 3. absence of either a type I or III endoleak; 4. patent endoluminal graft without significant twist, kinks, or obstruction (>30% luminal stenosis or a pressure gradient >10 mm Hg) by intraoperative measurements; 5 patency of both renal arteries and at least one hypogastric artery. Primary technical success can include the use of additional modular components, stents, angioplasty, and adjunctive surgical procedures. However, if unplanned endovascular or surgical procedures are necessitated it must be noted.

Clinical success requires the successful deployment of the endovascular device at the intended location without death as a result of aneurysm-related treatment, type I or III endoleak, graft infection or thrombosis, aneurysm expansion (diameter >5 mm, or volume >5%), aneurysm rupture, or conversion to open repair, occlusion of the renal arteries. The clinical success was measured at every follow-up interval. Any additional maneuvers, planned or unplanned, aimed to maintain clinical success must be carefully reported.

Secondary endpoints:

- Evaluation of the intra-operative and peri-operative (within 30 days) adverse events

- Collection of eventual adverse events related to the treatment procedure and eventual post-hoc analysis
- Evaluation of reintervention (time elapsed since index operation, type, and indication);
- Evaluation of potential risk factors (baseline, anatomical features, procedural technique) potentially related to adverse events
- Evaluation of the main procedural and fluoroscopy time, evaluation of the average contrast medium (CM) dose as well as Dose Area Product (DAP) (mGym3).

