Adverse events are defined as any systemic or local complication directly related to the procedure. Adverse events that occurred in the first 30-day were considered procedure-related, unless differently demonstrated.

Any surgical, open, or endovascular, procedure aimed to address adverse events was named re-intervention.

The secondary endpoints represent specific technical aspects related to the procedure and the endograft.

Treatment-related adverse events and re-interventions are important to state the safety of the procedure over time and its external reproducibility.

The procedure and fluoroscopy time, as well as the contrast-medium dose, will be used to evaluate the complexity of the procedure, comparing it with the same reported in the literature for standard EVAR.

Timeline

[figure not shown]
Months 1-3 Organization and logistic set-up.

Months 3-15 Subjects enrollment, data collection, treatments, clinical follow-up.

Months 15-18 Conclusion of recruitment, first (3 months) follow-up end for every patient, ad-interim analysis

Month 27-39 2-year follow-up end, mid-term analysis

Month 63-75 Conclusion of the follow-up, analysis of the results and their validation,

statistical analysis, project completion and analysis for further work, dissemination of the results

Gantt chart:

Sample size

No statistical analysis of the sample size was carried out. Considering the number of AAA responding to the inclusion criteria treated in the participating centers and the enrollment period (1 year) a sample size of 50 patients was estimated. This number should be sufficient to evaluate the endpoints reported in the appropriate section.

The estimated number of patients recruited for the present center is 15 patients

Recruitment

All the involved centers represent the third referral level of complex Abdominal Aortic Aneurysms.

For what concerns our center all patients affected by AAA responding criteria for treatment were evaluated at the Vascular Surgery Unit of the Azienda Ospedaliero Universitaria di Modena. Those meeting the inclusion criteria will be singularly recruited.

Taking into account a mean of 120 endovascular procedures on the abdominal aortic and 10 complex procedures with custom-made devices, a safety 12-month recruitment should be considered. The entire Medical staff of the department is informed about the present project and will refer the potential subjects to the Investigators.

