8. MANAGEMENT OF THE DATA

The collected data will be managed into a dedicated electronic case report form (CRF). The CRFs will be stored on a dedicated and validated website. Only the Investigators will have access to the data with a personal password. Only the PI and the first data manager will be able to see all the data, while the other investigators will have permission to manage only the data of the patients enrolled in their center.

To ensure the correct data collection two Investigators will perform the clinical and radiological assessment at each follow-up visit. Before the conclusion of the visit, a double-check will be performed by the Investigators. The CRF will be completed at the time of enrollment and each follow-up visit thereafter. The CRF required data are declared below.

A personal code will be generated at the enrollment. The CRF will be filled anonymously. The following anamnestic data: age, sex, comorbidities (hypertension, cardiopathy, hyperlipidemia, peripheral arterial disease, previous surgery, etc). Procedure planning details were detailed previously. The procedure details: planned and unplanned adjunctive procedure, the adverse events, the skin-to-skin time, the fluoroscopy time and DAP, the type of anesthesia, the dose, and characteristics of CM used. Primary and secondary endpoints will be registered as defined previously.

The following indicators will also be collected: time of recovery from the intervention and the number of an hour passed in the Intensive Care Unit if needed.

In case of the patient's voluntary withdrawal, the CRF will be discontinued. The patient will undergo standard clinical practice follow-up.

In case of device-related adverse-events, a detailed description of the event will be performed to inform the regulatory authority. The clinical follow-up and the CRF proceed as stated.

In case of death, the study personnel will investigate the cause and any eventual relation with the treatment or device will be declared to the regulatory authority and carefully reported on the eCRF.

Statistical methods

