Continuous variables will be expressed as mean, and standard deviation, and differences tested with the two-sided t-test or the Mann–Whitney U-test, if appropriate. Categorical variables will be expressed as counts and percentages and the chi-square test or Fisher's exact test will be used for analysis. All data will be entered into the logistic regression model if they had a univariable P-value of <0.05 . Data resulting significant in this model will be put in a multivariate one. In the multivariable analyses, clinical factors or potential confounding variables will be expressed as odds ratios with 95% confidence interval (CI). The goodness of fit of the logistic regression models will have been assessed by calculating the C-statistic. Survival analysis and freedom from adverse events will be assessed through the Kaplan-Meier analysis with their relative 95% CI. A P-value < 0.05 defined the statistical significance. The analysis was carried out using STATA 15.1 (StataCorp College Station, Texas, USA).

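### Risk factors for adverse events are modelled only by logistic regression, with no time window or time at risk, and the entry rule admits variables that can follow from the event

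*Combined protocol and SAP*

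**What the plan says.** Section 7 (Endpoints) lists as a secondary endpoint: "Evaluation of potential risk factors (baseline, anatomical features, procedural technique) potentially related to adverse events". Adverse events are procedure-related complications. The definition sets no time limit, although a separate secondary endpoint covers intra-operative and 30-day events. Section 6 sets follow-up of at least 5 years.

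Section 8 (Statistical methods) plans a univariable screen, then logistic regression, then a multivariable model reported as odds ratios. The entry rule is: "All data will be entered into the logistic regression model if they had a univariable P-value of <0.05". The threshold is general: "A P-value < 0.05 defined the statistical significance". The model's outcome, its time window and the handling of patients who die or withdraw are not given. The same paragraph treats these events as time-dependent: "Survival analysis and freedom from adverse events will be assessed through the Kaplan-Meier analysis with their relative 95% CI". No Cox or competing-risk model appears.

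Section 8 also lists the procedure data to be collected, among them "planned and unplanned adjunctive procedure, the adverse events, the skin-to-skin time, the fluoroscopy time and DAP", and adds recovery time and intensive-care hours. The form is discontinued when a patient withdraws. On size, section 7 says "a sample size of 50 patients was estimated" and "No statistical analysis of the sample size was carried out".

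**The concern.** There are two separate weaknesses.

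**Time at risk.** A yes/no outcome over 5 years ignores how long each patient could be seen to have an event. A factor such as age or comorbidity may raise the event rate and also shorten observation through death or withdrawal. Part of its effect on events then goes unseen, and the odds ratio moves towards 1. The interim analysis has a further source of unequal time: with enrolment in months 3–15, follow-up at month 18 runs from 18 − 15 = 3 to 18 − 3 = 15 months.

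**Order of cause and effect.** An intra-operative complication can prolong the operation, add fluoroscopy time or prompt an unplanned adjunct. If such variables are screened against adverse events, they can be reported as risk factors when they are results of the event. They then compete in the model with the baseline and anatomical factors.

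The stake is an exploratory secondary endpoint, not the primary one. It still matters, because sections 4 and 5 say the data will inform the case for a dedicated device.

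**Working it through.** The plan gives no event rate, loss rate or power, so there is no figure of its own to reproduce. From the documents: N = 50, 5 years, P < 0.05, screening by t-test or Mann–Whitney and by chi-square or Fisher. Everything else below is an assumption.

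**1. Expected odds ratio.** With constant event hazard h and loss (death or withdrawal) hazard c, the probability that an event is observed by 5 years is

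P = h/(h + c) × (1 − exp(−5(h + c))).

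The hazard is h = 0.06 without the factor and 0.12 with it (hazard ratio 2).

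| Loss per year, with / without factor | P with | P without | Odds ratio |
|---|---|---|---|
| none / none | 0.451 | 0.259 | 0.822/0.350 = 2.35 |
| 4% / 4% | 0.413 | 0.236 | 0.704/0.309 = 2.28 |
| 10% / 10% | 0.364 | 0.207 | 0.572/0.260 = 2.20 |
| 12% / 4% | 0.349 | 0.236 | 0.537/0.309 = 1.74 |

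Equal loss changes little. The drop to 1.74 needs a factor that also triples the loss rate.

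**2. Power.** Exact rejection rates of the likelihood-ratio test in a univariable logistic model, 25 against 25 patients: about 28% with 4%/year loss in both groups, and about 15% with 12% against 4%.

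**3. False positives.** The factor has no effect on events (h = 0.06 in both groups).
- Withdrawal 10% against 2%/year: P = 0.207 and 0.247, odds ratio 0.79, rejection rate 6.9%.
- Death 12% against 4%/year: P = 0.198 and 0.236, odds ratio 0.80, rejection rate 6.8%.
- No difference in loss: 5.4%.

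**4. Cross-check by simulation.** N = 50, half exposed, 5-year event risk 20–40%, 5-year loss or death 30% in the unexposed, 2,000 runs per setting. Power for a true hazard ratio of 2:

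| Hazard ratio for loss | Logistic | Log-rank |
|---|---|---|
| 1 | 22–38% | 22–37% |
| 2 | 13–20% | 20–34% |
| 4 | 6–7% | 19–32% |

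For a factor with no effect on events, logistic false positives were 5–6%, 6.1–6.5% and 10–16% in the same three settings.

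**5. Variables that follow from the event.** Assume 10 of 50 patients have an event and the variable has no causal role. The share of studies in which it passes P < 0.05 is:
- operating time 0.5 SD longer because of the event (t-test, 10 against 40): 28%;
- operating time 1 SD longer: 79%;
- unplanned procedure in 50% of patients with an event against 5% without (Fisher): 90%.

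The nominal rate is 5%.

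**The case against.** Several points on the other side are sound.

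- **Unequal loss is the driver.** A reader might infer that ignoring time at risk by itself turns a hazard ratio of 2 into 1.74, or creates false risk factors. It does neither. With loss unrelated to the factor, logistic regression and log-rank perform alike. Even the assumed null case of 10% against 2% withdrawal per year, which means 1 − exp(−0.5) = 39% against 1 − exp(−0.1) = 10% withdrawn by year 5, lifts false positives only to about 7%. No passage suggests loss that uneven.
- **Death is not simply censoring.** A patient who dies without an event never has one, so an odds ratio of 0.80 correctly describes lower cumulative incidence. It is wrong only against a cause-specific target, which the plan does not state. Withdrawal differs: the event may still occur and go unrecorded.
- **Handling is not stated.** One might infer that withdrawn patients will be counted as event-free. The documents do not say so; they leave outcome, window and handling open.
- **Mitigating text exists.** Refusal of follow-up is an exclusion, telephone contact is planned, and staggered entry creates no imbalance once everyone has reached 5 years. Clinical follow-up continues after withdrawal, but the form stops, so those data do not reach the analysis.
- **Section 7 narrows the candidates.** Its list arguably excludes intensive-care hours and recovery time, and procedure and fluoroscopy time have their own descriptive endpoint. However, the entry rule in section 8 is the operative one and is not limited to that list. Unplanned adjuncts and operating time can also pass as procedural technique.
- **Barring every operative variable would go too far.** A completed operative variable does precede a late event.

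**Conclusion.** The point holds in a limited form. The only regression planned for this endpoint has no time window and no time at risk, and nothing requires a predictor to precede the event. No other section repairs this.

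On time at risk, the main harm is missing real factors that also raise death or withdrawal: odds ratio 1.74 against 2.28 with equal loss and 2.35 with none, and power about 15% against 28%. This rests on the assumed 6%/year event hazard, hazard ratio 2 and loss of 12% against 4% per year. The documents do not support a claim that false risk factors are a large problem by this route.

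On predictors that follow from the event, passing the screen in 28–90% of studies depends on assumed effect sizes and 10 events. The flaw in the order of cause and effect does not. It is clearest for unplanned adjuncts and for operating and fluoroscopy time. It reaches intensive-care hours and recovery time only if section 8 is read literally.

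**What to change.** 1. Name the outcome and window of each model. Keep logistic regression with odds ratios for intra-operative and 30-day events, where follow-up should be nearly complete.
2. For later events, use a cause-specific Cox model with time from the index operation, penalised if events are few. Report hazard ratios, and give cumulative incidence where death competes.
3. Reconcile the entry rule in section 8 with the list in section 7 by admitting only predictors fixed before the event modelled. For intra-operative and 30-day events these are baseline data, CTA anatomy and planned technique. For later events, completed operative variables may be added. Keep the number of candidates in proportion to the expected events.
4. Report intensive-care hours and recovery time descriptively.

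The cost is wording in the statistical section. The planned Kaplan–Meier analysis already needs event and censoring dates, so no new data are required. The small downside is two models for one exploratory endpoint, each with few events. Estimates will stay imprecise: even log-rank reached only 19–34% power for a hazard ratio of 2 in the simulated settings where the factor also raised loss.

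### The risk-factor selection rule makes no provision for separation, so a binary factor present in every event can fail a significance step that a weaker factor passes

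*Combined protocol and SAP*

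**What the plan says.** Section 7 (Endpoints) lists as a secondary endpoint: "Evaluation of potential risk factors (baseline, anatomical features, procedural technique) potentially related to adverse events". The analysis that serves it is in section 8 (Statistical methods).

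- For categorical factors, "the chi-square test or Fisher's exact test will be used for analysis". Continuous factors have "differences tested with the two-sided t-test or the Mann–Whitney U-test, if appropriate".
- Factors with univariable P<0.05 enter a logistic regression model. Then: "Data resulting significant in this model will be put in a multivariate one".
- Multivariable results are given as odds ratios with 95% confidence intervals.
- "A P-value < 0.05 defined the statistical significance", but the section does not say whether the logistic P-value comes from a Wald, likelihood-ratio or other test. It also does not say whether the intermediate model holds one factor or several.

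Penalised or exact logistic regression is not mentioned, nor is any rule for zero cells. On size, section 7 says "No statistical analysis of the sample size was carried out" and "a sample size of 50 patients was estimated" from the expected caseload.

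**The concern.** A factor must be significant in a logistic model before it reaches the multivariable model. Ordinary logistic regression has no finite estimate when all events fall in one level of a binary factor. The standard error then grows without limit and the Wald P, which is the usual figure printed beside an odds ratio, moves towards 1. A factor that Fisher's test finds strongly associated is therefore judged non-significant at the next step. A somewhat weaker factor, with one event among the unexposed, is estimated normally and kept.

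That is a reversed ordering, not just low power, and it can occur with a single candidate factor. At stake are the separated factor's adjusted odds ratio and the adjustment of the other factors for it. Section 4 says the data are meant to inform a possible dedicated device, so a clear anatomical or technical factor should not drop out for a computational reason.

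**Working it through.** **Inputs.** From the documents: N=50 and alpha 0.05. Two-sided testing is stated only for the t-test and is taken to apply throughout. The plan's 50 has no formula behind it, so there is no figure to reproduce. The documents give no adverse-event rate for this cohort. The only rates quoted are in section 4: technical success 94% v 98% and type-Ia endoleak 10% v 2%, for hostile v favourable necks. Applied to 50 patients these give 1–3 and 1–5 events. All exposure splits and risks below are assumptions.

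**Example A: 5/15 exposed v 0/35 unexposed.**
- Fisher: C(15,5)/C(50,5) = 3,003/2,118,760 = 0.0014. Passes the screen.
- Ordinary odds ratio: (5×35)/(10×0), which is infinite. Run to convergence, the coefficient is about 20.5 with SE about 6,800, and both keep growing with further iteration. Other standard fitting routines gave Wald P from 0.978 to 0.9998. Wald P is thus 0.97 or more, and the factor fails.
- Likelihood ratio: the log-likelihood with the factor is 5 ln(1/3) + 10 ln(2/3) = −9.548. Without it, 5 ln(0.1) + 45 ln(0.9) = −16.254. The statistic is 2×6.706 = 13.41 on 1 df, P=0.00025.
- Firth: in a single 2×2 table this adds 0.5 to each cell, so OR = (5.5×35.5)/(10.5×0.5) = 37.2. Profile penalised-likelihood 95% CI 3.7 to about 5,000, P=0.0008.

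**Example B: one event moved, 4/15 v 1/35.**
- Fisher: (1,365×35 + 3,003)/2,118,760 = 0.024.
- OR = (4×34)/(11×1) = 12.4; SE = √(1/4+1/11+1/1+1/34) = 1.171; z = 2.515/1.171 = 2.15; Wald P=0.032. Kept.

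B has the weaker association by Fisher's test, yet B passes and A does not.

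**How often.** All 2×2 tables with 10, 15 or 25 of 50 exposed were enumerated exactly. The figure taken is the share with a zero cell that causes separation, among tables significant by Fisher's test in the direction of higher risk in the exposed.

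| Assumed risks (unexposed; exposed) | Odds ratio | Expected events | Share separated |
|---|---|---|---|
| 2–5%; 30–40% | 8.1–32.7 | 3.8–11.2 | 16–68% |
| 10% with 30–50%, or 15% with 40–50% | 3.8–9.0 | 7.0–16.2 | 0.4–19% |

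The odds ratio is [p1/(1−p1)]/[p0/(1−p0)], where p1 and p0 are the exposed and unexposed risks; for example (0.30/0.70)/(0.05/0.95) = 8.1. Expected events are n1·p1 + n0·p0; for example 10×0.30 + 40×0.02 = 3.8. Adding 15% v 30%, where the odds ratio is (0.30/0.70)/(0.15/0.85) = 2.4, leaves the second range unchanged.

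The unexposed risk drives the result. With 35 unexposed, the chance of no unexposed event is 0.98^35 = 0.49 at a risk of 2%, 0.95^35 = 0.17 at 5%, and 0.90^35 = 0.025 at 10%.

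A separate simulation by overall event rate (30% exposed, true odds ratio 10) agrees. Among Fisher-significant factors, 72% were separated at a 6% event rate, 43% at 10% and 6% at 20%.

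**The case against.** A reader might infer that the rule is wrong as written and that the strongest risk factor is the one it discards. The documents do not support that, for these reasons.

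- **The test is not named.** Nothing in section 8 says Wald. A likelihood-ratio test would keep example A (P=0.00025). This stands. Even so, the odds ratio and upper limit promised for the multivariable model would not be finite, so the gap remains under either test.
- **A zero cell is needed.** A strong factor with even one unexposed event is handled normally, as example B shows. A continuous factor is affected only if it splits the events perfectly, and many candidates are continuous (age, diameters, lengths, angles). This stands.
- **The frequency is assumed.** The 2–10% rates in section 4 are for technical failure and one endoleak type. The endpoint covers any procedure-related complication, and follow-up is at least 5 years. If pooled events reach about 20%, separation is uncommon. This stands, although single event types would be sparser.
- **The factor does not vanish from the report.** Counts, percentages and the chi-square or Fisher result are still planned, so a 5/15 v 0/35 split would be visible. This stands.
- **The remedy is partial.** With about five events no multivariable model is well supported under any estimator, and Firth leaves the P-value screening in place. This also stands, and the interval of 3.7 to about 5,000 shows it.

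The named software might omit a perfectly predicting factor, and perhaps its event-free stratum (35 of 50 patients in example A), rather than print a P near 1. The documents do not say how this would be handled and it was not tested. The factor's adjusted estimate would be lost either way.

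**Conclusion.** The point holds in a conditional form. Under separation, and with the usual Wald output, the second selection step rejects a factor that the first step finds strongly associated, and keeps a weaker one. The plan has no method that yields a usable estimate in that case. The arithmetic of the reversal is certain; its frequency is not. It ranges from under 1% to about two thirds of Fisher-significant binary factors across the assumed risks, and is high only when events are rare among the unexposed and the effect is large.

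The primary endpoint is untouched and the univariable finding survives, so this is a cheap improvement to one secondary endpoint: worth considering, not a fault that undermines the study.

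**What to change.** In section 8 (Statistical methods), state that the logistic models for the risk-factor endpoint will be fitted by Firth penalised likelihood, with profile penalised-likelihood P-values and 95% confidence intervals. Exact logistic regression with exact P-values and intervals is an acceptable alternative. Add that no factor will be dropped because its ordinary odds ratio could not be estimated, and label these results exploratory.

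The cost is a sentence or two of text and a different estimation command, with no new data. The downside is very wide intervals for sparse factors, which reflect how little the data say. The change does not remove the limits of P-value screening with few events.
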